1.2.2.3 Itraconazole and Hedgehog Pathway Inhibition

Pre-clinical and emerging clinical data suggest that itraconazoleis a potent inhibitor of the Hedgehog pathway. In a drug screen study of ~ 2400 FDA-approved or post-phase I drugusing a cell line containing a stably integrated *GLI1*-luciferase reporter which responds to exogenous stimulation by Sonic hedgehog signaling protein (SHH), itraconazole was identified as a potent inhibitor of the Hh pathway with an IC₅₀ of approximately 800 nM,greater than 10-fold more potent than that of ketoconazole (see figure 3 below) [29].

Figure 3. Itraconazole Potently Inhibits Hedgehog Pathway Relative to Other Azoles

Further experiments in *PTCH*-null and mutant *SMO* cell lines indicate that itraconazole inhibits the Hh pathway via a mechanism distinct from its effects on sterol biosynthesis by acting as an inverse agonist of *SMO*, thereby preventing its accumulation within the primary cilium. In a follow up study using a mouse xenograftmedullablastoma model with constitutively active Hhsignaling, itraconazole inhibited the growth of tumor allografts at steady-state serum concentrations comparable to those of patients treated with 200-300 mg PO BID on a chronic basis for fungal infections (see figure 4 below) [29].

Figure 4.Itraconazole Inhibits In Vivo Growth of a MedulloblastomaXenograft

In a recently presented phase II open label study of 19 patients with basal cell carcinoma, treatment with itraconazole (dosed at either 200 or 400 mg/day) led to a 23% reduction in clinical tumor area and a 65% reduction in Hedgehog activity as assessed by *GL11* mRNA expression [30]. In an intriguing correlative study from the previously described phase II trial of low- and high-dose itraconazole in patients with CRPC, modulation of Hh pathway activity was assessed by serial skin biopsy. Tissue samples were assayed for *GL11* mRNA expression by qRT-PCR, using previously validated methods [25]. In this analysis, 33% of patients treated with itraconazole 200 mg/day and 68% of patients treated with 300 mg PO BID experienced a decrease in*GL11* expression [31]. Interestingly, *GL11*downregulation appeared to be associated with an improvement in PSA progression-free survival, the primary endpoint of the study (see figure 5 below).

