2.0 Hypothesis and Study Objectives

2.1 Hypothesis

A significantly greater proportion of patients treated withitraconazole will achieve at least a 50% decline from baseline in serum PSA after 12 weeks of therapy, as compared to a historical control based upon the PSA response proportion observed in prior phase II clinical trials of other non-castrating therapiesin men with biochemically relapsed hormone sensitive prostate cancer. Favorable results with respect to PSA modulation, along with parallel findings demonstrating acceptable toxicity, potent Hedgehog pathway inhibition, and absence of significant impact on serum hormone levels, would form the basis for the further study of itraconazoleas a potentially viable non-castrating treatment option for men with biochemically relapsed prostate cancer.

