3.0 Study Design

3.1 Overall Study Characteristics

This is a phase II, single arm study of itraconazole dosed at 300 mg PO BID in patients with noncastrate, non-metastatic, biochemically relapsed prostate cancer after prior definitive local therapy. Simon''s two stage minimax design will be followed for accrual and include an interim test for lack of efficacy (see Sections 10.2 and 10.4). There is a pre-specified stopping rule for safety after 10 patients have been treated for a minimum of 8 weeks of protocol therapy (see Section 10.4). Patients will remain on protocol therapy until the first occurrence of any of the following: PSA progression, as defined in Section 2, development of metastasis, unacceptable toxicity, initiation of non-protocol therapy, or patient/physician withdrawal from study. Patients will remain on study until development of metastasis, initiation of non-protocol therapy, or patient/physician withdrawal from study, whichever occurs soonest. The total study duration including follow up is expected to be 3 years from the date of first patient enrolled onto study.

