3.2.3 Correlative Endpoints

Endocrine Parameters

- Mean percent change from baseline in serum androgen levels, including serum testosterone, DHEA-S, and androstenedione, after 4 and 12 weeks of protocol therapy.
- Mean percent change from baseline in additional serum hormone levels, including ACTH, aldosterone, deoxycorticosterone (DOC), 11-deoxycortisol, and cortisol after 4 and 12 weeks of protocol therapy.
- Mean baseline and mean percent change in serum hormone levels among patients achieving $\geq 50\%$ decline from baseline in serum PSA after 12 weeks of itraconazole therapy and among those not achieving this decline.

Hedgehog Pathway (assessed by serial skin biopsies on protocol therapy and analysis of archived primary prostate cancer tissue including prior biopsy or prostatectomy specimen)

- Proportion of patients who display a down-regulation of the Hedgehog pathway, as assessed by measurement of *GL11* mRNA expression by RT-PCR on serial skin biopsies obtained at baseline and after 4 weeks of protocol therapy with itraconazole. Down-regulation will be defined as a decline of any magnitude in *GL11* mRNA expression after 4 weeks of protocol therapy compared to baseline expression level.
- Proportion of patients with and without at least a 50% decline from baseline after 12 weeks of protocol therapy in PSA exhibiting a down-regulation of the Hedgehog pathway.
- Median time to PSA progression between patients with and without down-regulation of the Hedgehog pathway on itraconazole therapy.
- Proportion of patients with and without at least 50% decline from baseline after 12 weeks of protocol therapy in PSA exhibiting over-activation of Hedgehog pathway components as assessed by immunohistochemical (IHC) and mRNA expression analysis of primary prostate cancer tissue (prior biopsy or prostatectomy specimen). Patients will be dichotomized (immunohistochemical staining 0 to 1+ vs. 2 to 3+ staining intensity; mRNA expression above and below median) for the purposes of analysis of the Hedgehog pathway in primary prostate cancer tissue.
- Median time to PSA progression between patients with and without Hedgehog pathway over-activation in archived primary prostate cancer tissue.

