10.8.3 Analytic Plan for the Correlative Objectives

Endocrine Parameters

Serum hormone levels, including testosterone, androstenedione, DHEA-S, cortisol, aldosterone, 11-deoxycortisol, ACTH, and deoxycorticosterone, will be measured at baseline, at week 4, week 12, and at the time of PSA or clinical progression. To summarize the outcome, descriptive statistics including the mean percent change from baseline in serum hormone levels at 4 and 12 weeks will be presented with a standard deviation and Pearson"s correlation will be used to estimate the relationship between the baseline hormone level and percent change in hormone level after 4 and 12 weeks of treatment. Analysis of variance (ANOVA) methods for mixed models allowing for variable number of follow-up measurements with linear contrasts will be used to evaluate the change in serum hormone levels after 4 and 12 weeks of protocol therapy. It is hypothesized that approximately 15% of patients treated with protocol therapy will achieve a PSA decline \geq 50%. Depending upon the observed frequency, the ANOVA model will include a factor to test for the effect of PSA decline on change in serum hormone levels. Otherwise, analyses will compare the baseline and percent change in serum hormone levels at 4 and 12 weeks between patients achieving a PSA decline $\geq 50\%$ or not using a two group t statistic. For these exploratory analyses, graphic presentations will also be used to explore the overall pattern of change in serum hormone levels between those with and without a PSA decline.

Hedgehog Pathway

The quantitative expression of *GLI1*, a downstream product of the Hedgehog signal transduction pathway, will be measured by quantitative RT-PCR from serial skin biopsies obtained at baseline and after 4 weeks of therapy. The fold change in expression level after 4 weeks of protocol therapy will be calculated for each patient. Descriptive statistics will be used to summarize the proportion of patients with down-regulation of *GLI1* expression after 4 weeks of treatment with itraconazole. Down-regulation will be defined as any magnitude of decrease in *GLI1* mRNA expression after 4 weeks of protocol therapy compared to baseline expression level. The patient

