cohort will be dichotomized by whether there is up- or down-regulation of *GL11* expression. Fisher's exact test will be used to test for an association between down-regulation of *GL11* expression and PSA decline 50% on protocol therapy. The probability distributions for each *GL11* expressionsubset (as defined above) of the time to PSA progression will be estimated using the Kaplan-Meier product limit method. The results will be summarized by the estimated median with 95% confidence intervals. An exploratory analysis using the log-rank test will be used to test for differences in the distributions between patients with down-regulation of *GL11* expression vs. those without *GL11* down-regulation on therapy.

The quantitative expression of *GLI1* will also be measured by quantitative RT-PCR from archived primary prostate cancer tissue. The patient cohort will be dichotomized by expression level of *GLI1* (above vs. below the median). Fisher's exact test will be used to test for an association between *GLI1* expression in primary prostate cancer tissue and PSA decline $\geq 50\%$ on itraconazole therapy. The probability distributions for each *GLI1* expression subset of the time to PSA progression will be estimated using the Kaplan-Meier product limit method. The results will be summarized by the estimated median with 95% confidence intervals. An exploratory analysis using the log-rank test will be performed to test for differences in the distributions between patients with *GLI1* expression above vs. below the median from primary prostate cancer tissue specimens.

Immunohistochemical analysis of primary prostate cancer tissue for protein expression of *PCTH1*, *GL11*, *SMO*, as well as Sonic hedgehog ligand will be carried out for patients with evaluable tissue. It is estimated that approximately 50% of patients will have tissue available for analysis. Immunohistochemical expression will be graded as 0, 1+, 2+, and 3+ staining intensity by independent, blinded pathologic assessment. For each protein, the patient cohort will be dichotomized based on intensity of IHC staining (0 and 1+ vs. 2+-3+). Fisher''s exact test will be used to test for an association between IHC expression and PSA decline > 50% on protocol therapy. The probability distibutions for each expression subset of the time to PSA progression will be estimated using the Kaplan-Meier product limit method. The results will be summarized by the estimated median with 95% confidence intervals.

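### GLI1 down-regulation counts a fall of any size and is only described, so it is weak evidence of Hedgehog inhibition and silent on potency; the fold change already computed should be analysed

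*Combined protocol and SAP*

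**What the plan says.** Sections 3.2.3 and 10.7.3 define the skin-biopsy endpoint by direction alone: "Down-regulation will be defined as a decline of any magnitude in" GLI1 mRNA between baseline and week 4. Section 10.8.3 repeats it: "Down-regulation will be defined as any magnitude of decrease in" expression.

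For the analysis, Section 10.8.3 states: "Descriptive statistics will be used to summarize the proportion of patients with down-regulation of" GLI1. It names no confidence interval, reference value or test for this proportion. It also states: "The fold change in expression level after 4 weeks of protocol therapy will be calculated for each patient". No summary of the size of that fold change follows, and no paired test.

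The formal tests that use the skin result are of another kind: "Fisher's exact test will be used to test for an association between down-regulation of" GLI1 and PSA decline, and a log-rank comparison of time to PSA progression between the up and down groups. Both ask whether the split goes with PSA outcome. Neither asks whether GLI1 fell.

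The result is given a role in the argument. Section 2.1 lists "potent Hedgehog pathway inhibition" among the findings that would support further study, and Section 5.3.3.2 gives pathway down-regulation a similar place. There is no control group: "This is a phase II, single arm study of itraconazole dosed at 300 mg PO BID".

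**The concern.** Any two measurements of the same quantity differ, and one of them is lower. A definition with no threshold therefore classes some men as down-regulated even if the drug does nothing. With no control arm, no replicate baseline biopsy and no stated assay variability, the documents give no way to tell how many.

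The proportion also discards size. A 5% fall and an 80% fall count the same, so the endpoint cannot speak to the potency that Section 2.1 names. Nor can it be set beside the 65% reduction in GLI1 expression that Section 1.2.2.3 cites from the basal cell carcinoma study, which is a magnitude.

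At stake is the mechanistic conclusion. A moderate proportion, reported without an interval or a reference, could be read as pathway inhibition when the data are compatible with none.

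**Working it through.** **Inputs from the documents.** Definition and analysis: Sections 3.2.3, 10.7.3 and 10.8.3. Evaluable patients: 40 (Section 10.2). Skin biopsy optional (Section 6.3.6). Earlier result in castrate-resistant disease at this dose: "68% of patients treated with 300 mg PO BID experienced a decrease" in GLI1 (Section 1.2.2.3); at 200 mg/day the figure was 33%. Denominators for the skin assay are not given.

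**Assumptions.** The number of paired biopsies is not stated; 20, 30 and 40 are used. Log2 fold change is taken as normal for the power comparison only.

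**Plan's own figures.** The documents give no sample size, power or reference rate for GLI1. The primary design does reproduce. With 22 then 40 patients, continuing on more than 2 responses and rejecting at 8 or more, the exact early-stopping probability at 10% is 0.620, alpha is 0.040, and power at 25% is 0.803. Nothing below touches it.

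**Step 1: rate of falls with no drug effect.** Let D be the week-4 minus baseline log2 expression, with mean m and standard deviation s. Under normality, P(D < 0) = Φ(−m/s). At m = 0 this is Φ(0) = 0.50 whatever s is. More generally, 0.50 needs only that the errors at the two visits are exchangeable and that nothing drifts.

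**Step 2: the proportion does not measure size.** With s = 0.5 and m = −0.25, P(D < 0) = Φ(0.5) = 0.69. With s = 1.0 and m = −0.5 it is again Φ(0.5) = 0.69. The typical falls are 1 − 2^(−0.25) = 16% and 1 − 2^(−0.5) = 29%. The same proportion fits both.

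**Step 3: chance results under a 50% null.** X ~ Binomial(n, 0.5).

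| Pairs | P(60% or more) | P(68% or more) |
|---|---|---|
| 20 | 0.25 (X ≥ 12) | 0.058 (X ≥ 14) |
| 30 | 0.18 (X ≥ 18) | 0.021 (X ≥ 21) |
| 40 | 0.13 (X ≥ 24) | 0.008 (X ≥ 28) |

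**Step 4: a repeat of roughly 68%.** Exact (Clopper-Pearson) 95% CI and two-sided p against 50%:

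- 14/20 (70%): 46% to 88%, p = 0.115
- 27/40 (67.5%): 51% to 81%, p = 0.038

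The smaller sub-study does not exclude 50%; the larger one just does.

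**Step 5: what the dichotomy costs.** A true proportion of 68% corresponds to a standardised shift of Φ⁻¹(0.68) = 0.468. Two-sided 5% power, with the sign test exact and the paired t test from the noncentral t with noncentrality 0.468√n:

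| Pairs | Sign test rejects at (upper side) | Sign test power | Paired t power |
|---|---|---|---|
| 20 | 15/20 | 34% | 51% |
| 30 | 21/30 | 49% | 70% |
| 40 | 27/40 | 60% | 82% |

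**Step 6: the plan's practice for other paired markers.** For PSA doubling time, Section 10.8.2 plans a paired t or Wilcoxon test. For hormones, Section 10.8.3 plans mean percent change with its standard deviation and mixed-model contrasts. For GLI1, also measured before and on treatment, neither is planned.

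**The case against.** The strongest case on the other side has four parts.

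- **The endpoint is correlative.** Its stated objective is to determine a proportion, Section 1.4 calls these findings exploratory, and no decision rule uses them. This stands, and it limits the point to the mechanistic reading.
- **The metric has a reason.** The earlier castrate-resistant study reported the proportion with any decrease, and Section 5.2.2 relies on it in choosing the dose. This stands as a reason to keep the proportion, but not as a reason to report it without an interval or to leave the fold change unanalysed.
- **The 50% figure is not in the documents.** It rests on exchangeable error without drift. Batch, biopsy site or time could move it either way, and a single arm cannot detect that. This stands, and a mean fold change tested against zero has the same weakness.
- **Random misclassification weakens the Fisher and log-rank associations.** It makes a real link with PSA outcome harder to find. It would not manufacture one.

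A reader might infer more: that the endpoint cannot show Hedgehog inhibition at all, or that a repeat of 68% would be noise. The documents support neither. A proportion well above 50% would be evidence of a shift under the stated assumption. Already at 27/40 the interval excludes 50%, and 68% or more has probability only 0.021 at 30 pairs and 0.008 at 40 under the null. It is the bare proportion, particularly a moderate one from few pairs, that is weak.

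**Conclusion.** The point holds as a limitation of a correlative analysis. As planned, the proportion with any fall in GLI1 has no interval and no reference, and the fold change that would show size goes unused. Assuming exchangeable error and no drift, the natural comparison is 50%, and 60% or more would arise by chance in 13% to 25% of trials with 40 down to 20 pairs. Testing log fold change instead of its sign would raise power by about 17 to 22 percentage points at a true 68%, if log fold change is roughly normal. The number of pairs is an assumption throughout. Potency cannot be read from the proportion at any sample size. The primary PSA test and its decision rule are not affected.

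**What to change.** In Section 10.8.3:

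1. Make the main summary the mean log2 fold change in GAPDH-normalised GLI1 (the normalised value is already derived under Section 9.2) with a 95% CI, and a paired t or Wilcoxon signed-rank test, the choice that Section 10.8.2 already allows for PSA doubling time.
2. Keep the any-decrease proportion for comparison with the earlier study. Give its number of pairs and an exact 95% CI, and read it against 50%.
3. State that the 50% reference, like the test of mean change against zero, assumes no drift between visits, and that a single arm cannot rule drift out.
4. As an exploratory addition, relate log2 fold change as a continuous variable to PSA response (two-group comparison of log2 fold change) and to time to PSA progression (Cox model). At the 10% to 25% response rates of Section 10.2, 20 pairs would include about 2 to 5 responders (0.10 × 20 to 0.25 × 20), so the response comparison should be presented as descriptive.

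The cost is SAP wording. No extra patients, biopsies or assays are needed, so this is a free improvement.

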2.2.2 Secondary Objectives

Clinical Activity

• To determine the median time to PSA progression from the start of protocol therapy with itraconazole among men with biochemically relapsed prostate cancer.

PSA progression will be defined as follows: (1) If no PSA decline is observed on therapy, PSA progression will be defined as an increase in serum PSA > 50% above the baseline PSA, and an absolute increase of > 2 ng/mL above baseline, confirmed by repeat measurement at least 2weeks later (2) If PSA declines on therapy, PSA progression will be defined as an increase in serum PSA > 50% above the nadir PSA on therapy, and an absolute increase > 2 ng/mL above the nadir, confirmed by repeat measurement at least 2weeks later.

- To determine the median time to clinical progression measured from the start of protocol therapy with itraconazole among men with biochemically relapsed prostate cancer. Clinical progression will be defined as the first occurrence of either the development of metastases or initiation of non-protocol therapy, and will exclude PSA-only progression.
- To determine the median metastasis-free survival measured from the start of protocol therapy in patients treated with itraconazole for biochemically relapsed prostate cancer.
- To determine the mean percent change from baseline after 12 weeks of protocol therapy compared with pre-treatment in PSA doubling time. The pre-treatment PSA doubling time will be determined based upon all PSA measurements obtained within 3 months prior to Day 1 of protocol therapy, with a minimum of three PSA measurements spaced at least 14 days apart.

Safety/Pharmacokinetics

- To characterize the safety profile of itraconazole in the biochemically relapsed hormone sensitive prostate cancer population, as graded by Common Toxicity Criteria (CTCAE) version 4.03 (14-JUN-2010).
- To determine the mean steady-state itraconazole and hydroxy-itraconazole serum levels after 4 weeks of therapy with itraconazole.

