4.2 Inclusion Criteria

- 1. Histologic confirmation of adenocarcinoma of the prostate
- 2. Biochemically relapsed disease with a rising PSA on at least two successive measurements at least two weeks apart after prior definitive local therapy (radical prostatectomy, external beam radiation, or brachytherapy) or combination of radical prostatectomy and radiotherapy (RT) with curative intent. If the confirmatory PSA value is less than the screening PSA value, then an additional test for rising PSA will be required to documents progression (see Figure below):

- 3. Prior primary or salvage radiation or not a candidate for salvage radiation due to patient preference or clinical assessment based upon disease characteristics and/or patient co-morbidities.
- 4. Minimum PSA:
 - If no prior androgen deprivation therapy (ADT) for biochemical relapse:
 - 1.0 ng/mL if prior radical prostatectomy with or without adjuvant/salvage radiation therapy, confirmed by repeat measurement at least 2 weeks later, or
 - Nadir + 2 ng/mL if prior RT alone without prior radical prostatectomy, confirmed by repeat measurement at least 2 weeks later
 - If prior ADT for biochemical relapse:
 - 4.0 ng/mL or > 2 ng/mL above nadir on prior cycle of ADT, whichever is higher, confirmed by repeat measurement at least 2 weeks later

- 5. No evidence of metastatic disease on imaging by whole body bone scan (technetium-99 or Na-F PET bone scan) and cross-sectional imaging of the abdomen/pelvis (CT or MRI) within 6 weeks of Day 1 of protocol therapy
- 6. Prior androgen deprivation therapy (ADT) with LHRH agonist and/or antagonist allowed for either (neo)adjuvant treatment with local therapy or for biochemical relapse
- 7. Last effective dose of LHRH agonist/antagonist "expired" > 3 months prior to study entry.
- 8. For example, a patient receiving LHRH agonist injection every 3 months would be eligible provided their last injection was > 6 months prior to Day 1 of protocol therapy. A patient receiving LHRH agonist injections every 4 months will be eligible provided last injection was >7 months prior to Day 1 of protocol therapy.
- 9. Serum testosterone level:
 - If no prior androgen deprivation therapy:
 - A single measurement greater than 150 ng/dL within 3 months of day 1 of protocol therapy
 - If prior androgen deprivation therapy (either in adjuvant or biochemical relapse setting):

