5.0 Study Rationale

5.1 Rationale for the Study Population

Patients with biochemically relapsed, non-castrate, non-metastatic prostate adenocarcinoma after prior definitive local therapy will be enrolled onto this study. Both patients without prior ADT for biochemical relapse, or those on the "off" phase of a cycle of intermittent ADT will be allowed to enroll on the current study. Though allowing prior ADT for BCR may add heterogeneity with respect to expected disease outcomeswithin the study population, the primary objective of the current study is to investigate whether or not itraconazole has significant biologic activity in this disease setting, as reflected by decline in serum PSA after 12 weeks of therapy. Prior ADT for BCR is not hypothesized to significantly decrease the chance of detecting

PSA decline on itraconazole therapy, though it is acknowledged that prior studies of intermittent ADT have shown that nadir PSA tends to be higher and "off" phase length shorter with successive cycles of intermittent ADT [9]. Furthermore, the role for non-hormonal agents in BCR may eventually fit within the framework of an intermittent ADT strategy, to lengthen the period "off" therapy. As such, including patients with prior ADT for BCR in the current study reflects this potential future application of these agents.

Patients with up to 15 months baseline PSADT can be enrolled onto the current study. Prior studies have shown that pre-treatment PSADT is an independent prognostic factor in the BCR disease setting, and patients with a progressively shorter PSADT have an increasing risk of distant metastases and prostate-cancer specific mortality [38, 39]. Patients with a slow PSA doubling time > 15 months may be more suited to observation alone or local salvage therapies, and as such will be excluded from the current clinical trial.

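### The two exploratory GLI1 comparisons of time to PSA progression use only an unadjusted log-rank test, although Day 1 PSA and pre-treatment doubling time affect that endpoint and are already collected

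*Combined protocol and SAP*

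**What the plan says.** Section 2.2.2 (repeated in 10.8.2) sets a two-part rule for PSA progression. Without a decline: "PSA progression will be defined as an increase in serum PSA > 50% above the baseline PSA", together with "an absolute increase of > 2 ng/mL above baseline". After a decline, both parts are counted from the nadir: "an absolute increase > 2 ng/mL above the nadir" is required in addition to the 50% rise.

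Section 4.2 sets entry PSA by treatment history. Without ADT for relapse the minimum is "1.0 ng/mL if prior radical prostatectomy with or without adjuvant/salvage radiation therapy", or nadir plus 2 ng/mL after radiotherapy alone. With ADT for relapse it is "4.0 ng/mL or > 2 ng/mL above nadir on prior cycle of ADT, whichever is higher". Doubling time (PSADT) may be anything up to 15 months, and Section 5.1 says of it: "Prior studies have shown that pre-treatment PSADT is an independent prognostic factor in the BCR disease setting".

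Section 10.8.3 compares time to PSA progression between men with and without skin GLI1 down-regulation: "An exploratory analysis using the log-rank test will be used to test for differences in the distributions between patients with down-regulation". A log-rank test, also called exploratory, is planned for archived-tissue GLI1 mRNA above versus below the median. No strata, covariates or Cox model are named there or elsewhere. The immunohistochemistry groups get Kaplan-Meier medians and no test of time to progression. PSA is measured on Day 1 (Section 6.3.1) and PSADT at entry is a listed baseline characteristic (Section 10.6); that list names PSA at diagnosis but not Day 1 PSA.

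**The concern.** GLI1 status is observed, not assigned, so nothing balances the groups for baseline PSA or PSADT. Both affect the endpoint directly: PSADT sets how fast PSA climbs, and below 4 ng/mL the absolute part of the rule sets how far it must climb. Because the entry minima differ by treatment history, baseline PSA will be spread across the range where this matters.

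Two things are at stake. If the groups are alike in these factors, the spread they cause is noise and the test loses power. If the groups differ, the test can show a difference that belongs to PSA or PSADT rather than to the Hedgehog pathway, or hide a real one. The results may be carried forward: Section 1.2.2.3 reports an apparent link between GLI1 down-regulation and PSA progression-free survival in castrate-resistant disease, and Section 5.3.3.2 sees the tissue analysis as a possible route to a predictive biomarker.

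**Working it through.** **1. The plan's own figures.** The only stated operating characteristics belong to the primary endpoint (Section 10.2): continue if more than 2 of 22 respond, reject if at least 8 of 40 respond, with rates of 10% and 25%. Exact binomial sums give early stopping 0.620, one-sided error 0.0398 and power 0.803. These agree with the stated 0.62, 0.05 (as an upper limit) and 80%. No power is stated for the GLI1 comparisons.

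**2. What the progression rule does.** For a man with baseline PSA B, no decline and steady exponential growth with doubling time D, the threshold is max(1.5B, B + 2). The two parts meet where 0.5B = 2, so B = 4. Ignoring visit spacing and confirmation,

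time = D × log2(max(1.5, 1 + 2/B)).

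| B (ng/mL) | Threshold | Doublings | D = 6 months | D = 15 months |
|---|---|---|---|---|
| 1.0 | 3.0 | 1.585 | 9.5 | 23.8 |
| 2.0 | 4.0 | 1.000 | 6.0 | 15.0 |
| 3.0 | 5.0 | 0.737 | 4.4 | 11.1 |
| 4.0 | 6.0 | 0.585 | 3.5 | 8.8 |
| 10.0 | 15.0 | 0.585 | 3.5 | 8.8 |

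The largest ratio from baseline PSA is 1.585 / 0.585 = 2.7; above 4 ng/mL there is no further dependence. PSADT acts everywhere: at B of 4 or more, time runs from 1.8 months (D = 3) to 8.8 months (D = 15).

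**3. Error rate and bias.** Simulation, 1,000 runs per setting. Assumptions not in the documents: median PSA 3 ng/mL (log-SD 0.8, floor 1); median PSADT 6 months (log-SD 0.5); on-treatment doubling time varying around the pre-treatment value (log-SD 0.3); censoring uniform over 6–30 months. From the documents: the PSADT cap of 15 months, four-weekly PSA, and the group sizes (40 men split 68:32, after the down-regulation rate in Section 1.2.2.3, or 20 split evenly). The comparator is a log-rank test stratified at PSA 4 ng/mL and PSADT 6 months. Percent rejecting at two-sided 5%:

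| Setting | n = 40 unadjusted | n = 40 stratified | n = 20 unadjusted | n = 20 stratified |
|---|---|---|---|---|
| No effect, groups alike | 5.9 | 6.5 | 5.3 | 6.2 |
| No effect, ln PSA differs by 0.5 | 12.1 | 6.0 | 10.1 | 5.2 |
| No effect, ln PSA differs by 1.0 | 37.0 | 14.1 | 24.5 | 9.0 |
| No effect, ln PSADT differs by 0.5 | 44.0 | 14.7 | 29.9 | 9.0 |
| True 1.5-fold slowing, groups alike | 36.5 | 55.9 | 22.9 | 29.3 |

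With groups alike, the unadjusted test is close to nominal. Stratifying reduces the excess when they differ but does not always remove it.

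**4. Power with a Cox model.** Similar assumed spreads, true 1.5-fold lengthening of doubling time, model with log PSA and log PSADT:

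- 15 versus 15, PSADT known exactly: about 34% for log-rank, about 75–80% adjusted.
- 15 versus 15, PSADT estimated from three values with 10–15% PSA noise: about 34% for log-rank, about 43–54% adjusted. Within single runs the change was 37% to 54% at 10% noise and 31% to 43% at 15% noise.
- 15 versus 15, 10% noise and a wider individual response (log-SD 0.5): 26% to 36%.
- 10 versus 10, noisy PSADT: 22–24% for log-rank, 34–38% adjusted.

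Adjusting for PSA alone gave 41% at 10% noise and 39% at 15% noise, so the gain comes from both covariates.

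**5. How much data there will be.** Tissue is expected from about 50% of 40, so about 20 men; skin biopsy is optional and its number is not given. Even if all 20 progress, Schoenfeld's formula for a hazard ratio of 0.5 and an even split gives √(20 × 0.25) × ln 2 − 1.96 = 1.55 − 1.96 = −0.41, a power of 34%.

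**The case against.** The strongest reply is that nothing here is an error. The tests are labelled exploratory, no decision rests on them, and an unadjusted log-rank test is conventional for a biomarker split. Section 5.3.1 already acknowledges that time to PSA progression varies between patients. With groups alike, the test's error rate is about nominal. All of this stands, and it fixes the severity.

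Four limits on size also stand:

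- The 2 ng/mL part binds only below 4 ng/mL, so men with prior ADT for relapse are untouched by it unless their PSA falls.
- The formula covers men without a decline. Section 1.2.3.1 reports some PSA decline in 54% of the high-dose group in castrate-resistant disease; for decliners the nadir replaces the baseline.
- PSADT may rest on three values within three months (Section 4.2). Section 1.3.3 reports that 40% of placebo men in the rosiglitazone trial had PSADT lengthen beyond 150% of baseline, so the covariate is noisy.
- A Cox model on about 20 men is fragile and should not displace the planned test.

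The reply fails on one point: calling an analysis exploratory does not make unadjusted groups comparable. With no multiplicity adjustment planned, fixing two covariates in advance also prevents choosing them after the data are seen.

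**Conclusion.** The point holds as a low-cost improvement to two analyses. Time to PSA progression depends on baseline PSA below 4 ng/mL (up to 2.7-fold at equal growth, in men without a decline) and on PSADT throughout, and neither GLI1 comparison accounts for them. If GLI1 status is unrelated to both, the cost is power: about 10 to 17 percentage points at 15 versus 15 with a noisy PSADT. These figures rest on assumed spreads, noise and censoring.

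A reader might infer more than the documents support:

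- *That the log-rank test is invalid.* It is not. Bias requires the groups to differ in PSA or PSADT. For tumour tissue there is indirect support: Section 1.2.2.2 cites raised Hedgehog target genes in 70% of Gleason 8–10 against 22% of Gleason 3–6 tumours. For skin GLI1 the documents give none.
- *That adjustment more than doubles power.* That needs PSADT to be known without error.
- *That every Hedgehog comparison is affected.* The immunohistochemistry groups have no log-rank test.
- *That the progression definition or the primary analysis is at fault.* Neither follows; the primary endpoint and sample size are untouched.

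**What to change.** In Section 10.8.3, for the skin and archived-tissue GLI1 comparisons only, keep the log-rank test and pre-specify beside it a Cox model containing the GLI1 group, log Day 1 PSA and log pre-treatment PSADT. Add no further covariates, given about 20 men with tissue. Report the adjusted hazard ratio with its 95% confidence interval, as exploratory. Leave the progression definition as it is. Add Day 1 PSA to the baseline characteristics in Section 10.6.

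The cost is a few sentences of SAP wording. No new visits, samples or patients are needed.
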